Pilocarpine, a parasympathomimetic agent, is a glaucoma medication that works by causing contraction of the ciliary muscle leading to opening of the trabecular meshwork[3]. Due to its frequent dosing requirement and large number of ocular and systemic side effects, pilocarpine has largely fallen out of favor for the treatment of primary open angle glaucoma (POAG), except in patients for whom few other alternatives exist. However, pilocarpine is often used after trabectome surgery. The rational for its use after Trabectome procedure is for its miotic effect, which theoretically may prevent the formation of peripheral anterior synechiae. Formation of peripheral anterior synechiae can lead to the closure of the cleft that is generated and the possibility of failure of the procedure. While the theoretical benefit of pilocarpine has been proposed, its actual benefit has never been proven. In this study, we aim to evaluate whether Trabecome / Cataract surgery without pilocarpine is non-inferior to Trabecome / Cataract surgery procedure followed by treatment with pilocarpine. The outcomes to be evaluated are the degree (percentage) of IOP lowering from baseline after the procedure, the mean post-operative IOP, the number of IOP lowering agents required to achieve goal IOP, and the rate of progression towards further glaucoma surgeries.

Key Questions

1. What are the demographics and characteristics of patients undergoing combined cataract/trabectome surgery at Montefiore Medical Center?
2. What is the post procedure percent IOP drop at 1 month, 6 months and 1 year after surgery.

3. What is the number of pre and post procedure drops required to achieve goal IOP at 6 months, 1, 2 and 3 years after combined cataract/trabectome surgery in patients treated with post-op pilocarpine vs control?
4. What is the rate of progression towards further surgery in patients treated with post-op pilocarpine vs control over a 3 year follow up period?
5. What is the rate of pilocarpine related side effects and drug discontinuation due to adverse effects?

Objectives

1. To determine whether Trabectome/cataract surgery without pilocarpine is non-inferior to Trabecome / Cataract surgery procedure followed by treatment with pilocarpine in decreasing IOP at 1 year after surgery.
2. To determine the incidence and characteristics of pilocarpine induced side effects in this population.

Selection of Patients

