1. Inclusion Criteria: Patients with ocular hypertension or open angle glaucoma undergoing combined cataract surgery with trabectome in a single surgical center at Montefiore Medical Center with a single provider between March 1st 2018 and July 1st 2020
2. Exclusion Criteria: Patients with previous history of eye surgeries (including laser procedures).
3. Age Range: 30 to 100 years old

Study Design

Prospective randomized controlled trial

Study Methods

140 consecutive patients with POAG who are planned for combined cataract/trabectome surgeries will be consented for inclusion in this study. Patients will be randomized to one of two study arms, using an online computer randomizer; the first group labeled “treatment group” and the second “control group.” The treatment group will receive post-operative treatment with pilocarpine 2% for 1 month postoperatively, in addition to the standard post-operative surgical drops including topical steroids and topical antibiotic drops. The control group will receive the usual post-operative drop schedule without pilocarpine. Most surgeons who do combined trabectome/cataract surgery will include the use of pilocarpine besides steroid and antibiotic. However, it is also acceptable for patients to only receive steroid and antibiotics (without pilocarpine) after such surgery. Patients in both groups will be followed for 1 year with the primary endpoint of percent decrease in IOP after surgery at 1 year. Secondary outcome measures will include: progression of glaucoma on OCT and HVF testing, medication side effects, number of pre and postoperative drops the patient was using before and after surgery, and need for further glaucoma surgery. All subsequent visits will be according to routine post-operative monitoring, where visual acuities, intraocular pressures, gonioscopy measurements will be performed at the slit lamp. These visits will coincide with standard of care post op follow up visits.

Participant recruitment

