3. Feasibility of study – Over the time period 2/2016 – 9/2017, [name] completed 118 combined cataract/trabectome surgeries. Based on her historical usage and her usage of the combined procedure only increasing due to its success, we believe 140 patients can be recruited over a 1.5 – 2 year time frame.

Analytic Plan

All analyses will be based on the intent-to-treat approach (ITT). Standard descriptive statistics will be used to summarize the baseline characteristics and outcomes of the two treatment arms. The primary endpoint, percent decrease in IOP at 1 year after surgery compared to baseline, will be analyzed by computing the mean difference of this endpoint between treatment groups (pilocarpine - no pilocarpine) along with the corresponding two-sided 95% confidence interval. Non-inferiority of treatment without pilocarpine will be declared if the upper limit of the two-sided confidence interval is less than the margin of non-inferiority, which is deemed to be 5% in this study. Since the ITT approach can be anti-conservative in non-inferiority trials, a per-protocol analysis will also be performed. Two sample tests of the standard null hypothesis of no difference between groups will be conducted using the student T-test

for continuous variables or chi-square test for categorical variables (e.g., occurrence of side effects, need for further surgery). Linear or logistic regression models will be fit to the data to adjust for any baseline characteristics which are found to differ between treatment arms. In addition, generalized linear mixed models will be fit to the repeated measures obtained post-surgery, as part of every standard clinic encounter during follow-up, to assess whether the longitudinal trends in the outcomes differ between groups.

Sample size considerations

The sample size for this study is 140 subjects (70 per group). This sample size will yield greater than 95% power at a 1-sided Type I error rate of 2.5% (two-sided of 5%) to declare non-inferiority of the no pilocarpine group to the pilocarpine group with respect to the percent decrease in IOP after surgery, assuming an alternative hypothesis of no difference between groups, a non-inferiority margin of 5%, and a SD of 7.5% in both groups based on prior studies.

Data and Safety Monitoring Policy

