As pilocarpine is an FDA approved medication with the overall risk level to the patient deemed to be mild, DSM will be undertaken by the investigator. At each office visit over the course of the life of the study (all visits as part of standard of care) specific attention will be made to reviewing whether the patient is having any potential side effects of the medication. If any side effects are noted and either the side effect cannot be tolerated by the patient or it is deemed to not be safe for the patient to continue to use the medication, the medication will be stopped and the patients inclusion in the study terminated.

1. Hu, K., et al., *Ab interno trabecular bypass surgery with Trabectome for open angle glaucoma*. Cochrane Database Syst Rev, 2016(8): p. Cd011693.
2. Mizoguchi, T., et al., *Clinical results of Trabectome surgery for open-angle glaucoma*. Clin Ophthalmol, 2015. 9: p. 1889-94.
3. *Isotox Carpine (pilocarpine)[Package insert]*: Alcon, Inc. TX. 2010

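### Patients who stop pilocarpine for side effects are removed from the study, which contradicts the ITT analysis and can happen in only one arm

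*Combined protocol and SAP*

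**What the plan says.** - **Data and Safety Monitoring Policy.** Side effects of the drug are reviewed at each office visit. If one cannot be tolerated or is judged unsafe, "the medication will be stopped and the patients inclusion in the study terminated".
- **Study Methods, arms.** "The treatment group will receive post-operative treatment with pilocarpine 2% for 1 month postoperatively". For the comparator, "The control group will receive the usual post-operative drop schedule without pilocarpine".
- **Study Methods, follow-up.** "Patients in both groups will be followed for 1 year with the primary endpoint of percent decrease in IOP after surgery at 1 year".
- **Analytic Plan.** "All analyses will be based on the intent-to-treat approach (ITT"). It then adds: "Since the ITT approach can be anti-conservative in non-inferiority trials, a per-protocol analysis will also be performed".
- **Key Questions, item 5.** "What is the rate of pilocarpine related side effects and drug discontinuation due to adverse effects". Discontinuation is therefore foreseen, though no expected rate is given.

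The protocol describes no follow-up after the drug is stopped, no method for a missing 1-year IOP in the primary analysis, and no dropout allowance in the sample size.

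**The concern.** The safety rule ties two separate decisions together: stopping the drug and leaving the study. ITT depends on keeping them apart, because it compares arms as randomised whatever happened to treatment afterwards.

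The medication in the rule is pilocarpine, and controls never receive it, so they cannot meet the trigger. Ordinary loss to follow-up may occur in either arm. This loss is different: it is written into the protocol, it depends on treatment, and it falls on one side. It is exclusion after randomisation, selected on tolerance of the drug, in the comparison that carries the non-inferiority claim.

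The planned safeguard fails too. The per-protocol analysis is there because ITT may be too lenient in a non-inferiority trial. If terminated patients are already missing from the ITT set, both analyses lack the same people, and agreement between them gives no reassurance on this point. The mixed models in the Analytic Plan address longitudinal trends, not the primary test, and could use only the early visits of these patients.

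For Objective 2, the later course of symptoms after stopping would also go unrecorded.

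**Working it through.** **Inputs from the protocol.** 70 per group; SD 7.5 points; margin 5 points; one-sided alpha 2.5%; true difference zero; stated power above 95% (Sample size considerations). The difference is pilocarpine minus no pilocarpine, and non-inferiority is declared if the upper 95% limit is below 5 (Analytic Plan).

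**Assumed inputs.** The protocol gives neither of these:
- *d*, the share of the pilocarpine arm terminated: 10% and 20%.
- *D*, the mean 1-year percent IOP decrease in terminated minus retained patients: ±5 and ±10 points.

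**Step 1: reproduce the stated power.** SE = 7.5 × √(1/70 + 1/70) = 1.268. The noncentrality is 5/1.268 = 3.94 on 138 df, and the noncentral t gives 97.5%. The stated figure is right for 70 v 70.

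**Step 2: loss of numbers alone (D = 0).** SE = 7.5 × √(1/70 + 1/n), where n is the number retained on pilocarpine.

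| Retained v controls | SE | Power |
|---|---|---|
| 70 v 70 | 1.268 | 97.5% |
| 63 v 70 (10% lost) | 1.302 | 96.8% |
| 56 v 70 (20% lost) | 1.345 | 95.8% |
| 49 v 70 (30% lost) | 1.397 | 94.4% |

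Power drops below 95% only when 51 or fewer remain, that is, when at least 19/70 = 27% are lost. Precision is not the main problem.

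**Step 3: bias.** The mean of the whole pilocarpine arm equals the retained mean plus d × D. The retained-only difference is therefore off by −d × D:
- Smallest case: 0.10 × 5 = 0.5 points; 0.5/5 = 10% of the margin.
- Largest case: 0.20 × 10 = 2.0 points; 2.0/5 = 40% of the margin.

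**Step 4: effect on the test** (noncentral t, using the SEs above). If D > 0, the pilocarpine mean is understated and the shift favours declaring non-inferiority; the figure that matters is the type I error when the true difference is 5. If D < 0, the shift works against declaring it; the figure that matters is power when the true difference is zero.

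| d | Size of D | Shift | Type I error if D > 0 (nominal 2.5%) | Power if D < 0 (planned 97.5%) |
|---|---|---|---|---|
| 10% | 5 | 0.5 | 5.7% | 92.9% |
| 10% | 10 | 1.0 | 11.5% | 86.2% |
| 20% | 5 | 1.0 | 11.1% | 83.9% |
| 20% | 10 | 2.0 | 31.4% | 60.0% |

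**The case against.** **The size is assumed.** This is correct. No discontinuation rate or outcome gap is given, and the protocol rates the overall risk as mild. A gap of 5-10 points is 0.67-1.33 SD, which is large for patients who differ by their tolerance of a 1-month course. With 5% terminated and a 2.5-point gap, the shift is 0.05 × 2.5 = 0.125 points, or 2.5% of the margin. The tables are scenarios, and the effect could be close to zero.

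**The direction may be conservative.** Background suggests pilocarpine might prevent synechiae and failure of the procedure. If it does, patients who stop early would tend to do worse, and dropping them would make non-inferiority harder to show. But Background also says the benefit is unproven, and selection could run the other way. False non-inferiority is not shown to be the likely result, nor is it ruled out.

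**A clinical IOP may still exist.** Visits are standard of care, so a 1-year reading may be in the chart, and Study Methods promises 1 year of follow-up for both groups. This stands as a limit: what is lost, read literally, is the right to use the value in the study. It also shows how easily the conflict can be removed.

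**Objective 2 is mostly intact.** The event that triggers termination is seen before the patient leaves, so rates of side effects and of discontinuation can still be computed. Only the later course is lost.

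None of this reconciles the safety rule with ITT, and no other section does so.

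**Conclusion.** The concern holds, and the point must be fixed. Data and Safety Monitoring Policy conflicts with the Analytic Plan and with the 1-year follow-up in Study Methods. Applying the rule as written would replace the randomised comparison with one selected on tolerance of pilocarpine, and neither planned analysis set would expose it. This conclusion rests on the text and does not depend on the assumed rates.

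The size does depend on them: 0.5-2.0 points against a 5-point margin for 10-20% terminated and a 5-10 point gap, near zero if few patients stop or they resemble the rest, and of unknown sign. The stated power is correct for full follow-up, and the lost numbers would bring it below 95% only at about 27% loss or more. Severity rests on the one-sided exclusion: outcomes that the study has not collected cannot be recovered by later analysis.

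**What to change.** Reword Data and Safety Monitoring Policy so that stopping pilocarpine does not end study participation:
- A patient who stops the drug stays in the study. IOP, number of drops, further glaucoma surgery and symptoms are recorded at the standard-of-care visits through 1 year, unless the patient withdraws consent.
- The date of and reason for stopping are recorded, which also serves Key Question 5.
- In the Analytic Plan, state that these patients are analysed in their randomised arm under ITT and excluded only from the per-protocol set.

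The clinical decision on when to stop the drug is left as it is.

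**Cost.** A short protocol amendment and no added visits. With all 70 per arm giving a 1-year value, power stays at 97.5% and this rule introduces no selection bias. Check whether the consent form describes termination in the same terms and needs matching wording; that cannot be told from the protocol text.
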